2.2 Secondary Objectives

- To assess the safety of combining DEB-TACE with durvalumab and tremelimumab in patients with intermediate stage HCC.

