3. STUDY DESIGN

This is an open-label, single institution, single arm study of combination treatment of durvalumab and tremelimumab in patients with intermediate stage HCC (BCLC B) undergoing trans-arterial chemoembolization.

Patients will be recruited from the Johns Hopkins Multidisciplinary Liver Cancer Clinic, general liver clinic, inpatient admissions with newly diagnosed HCC, and direct referrals to Interventional Radiology for DEB-TACE treatment. Once their diagnosis and staging is confirmed in Liver radiology tumor board as intermediate stage, patients will be screened for enrollment.

Enrolled patients will proceed with DEB-TACE procedure along with pre-treatment biopsy of tumor and surrounding non-tumor tissue. Following their DEB-TACE procedure, patients will be followed in 7-10 days in hepatology clinic with labs for any new decompensating signs or symptoms. If the patient does not have any ongoing new decompensation, they will proceed with a 2nd biopsy, followed by 1st infusion of durvalumab 1500mg and tremelimumab 300mg 2 weeks after DEB-TACE. This will be followed by durvalumab 1500mg q4weeks until progression of disease, the end of study, or maximum 13 cycles.

All patients will receive repeat DEB-TACE every 8 weeks if there is residual tumor that can be targeted. A third biopsy will be done after 2 doses of durvalumab infusion during their second DEB-TACE procedure at week 8, unless the patient has CR.

Patients will have an MRI (or CT if contraindicated) at Week 6 and Week 14, then every 3 months unless additional DEB-TACE is needed. Patients who are clinically stable at initial disease progression may continue to receive study treatment until PD is confirmed on a follow-up scan (confirmed PD) if they do not show any significant toxicities. Patients will get a confirmatory scan, following the assessment of PD, at the next scheduled visit. Patients will continue to receive durvalumab and tremelimumab with the same dose and schedule as they were treated with initially.

Additionally, 20 patients from the institutional database will be selected as exact matched control based on age, gender, tumor stage and Child-Pugh score. We will evaluate the objective response rate (ORR) in comparison to the study group, using McNamer paired-sample test.

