5.2.1 Treatment regimens

All patients in this study will receive durvalumab and tremelimumab 2 weeks after initial DEB-TACE treatment. Patients will subsequently continue with their combination immunotherapy, while receiving DEB-TACE Q8W. Patients will only receive repeat DEB-TACE if there is residual tumor that can be targeted.

[figure not shown]
[figure not shown]

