6.2 Dosage and administration

6.3 Definition of Unacceptable Toxicity

The combination of tremelimumab and durvalumab has been previously tested in a dose-escalation study performed by AstraZeneca employing dose ranges of 1-10mg/kg q4weeks (tremelimumab) and 10-20mg/kg q2-4weeks (durvalumab). Patients treated in the 20 mg/kg durvalumab + 1 mg/kg tremelimumab group had the fewest AEs, Grade ≥ 3 AEs, SAEs, and treatment discontinuations due to AEs, but still showed strong evidence of clinical activity. This cohort had a lower number of treatment-related Grade ≥ 3 AEs or treatment related SAEs. No dose-limiting toxicities were reported. This is the dose level we will be administering for this study. Also, PK analysis indicated only minor impact of body weight (WT) on PK of both agents so to minimize errors and for ease of use the company have moved to a fixed-dose schedule of 1500 mg Q4W durvalumab (equivalent to 20 mg/kg Q4W) and 75 mg Q4W tremelimumab (equivalent to 1mg/kg Q4W).

Unacceptable toxicities will be evaluated from the time of first administration of durvalumab or tremelimumab until the Week 6 evaluation (prior to the second dose of durvalumab). Patients who do not remain on the study through the completion of this safety run-in period for reasons other than DLT will be replaced with another patient (see **Section 11.2.4** for details of safety run-in). Grading of unacceptable toxicities will follow the guidelines provided in the Common Terminology Criteria for Adverse Events (CTCAE) version 5.0.

An unacceptable toxicity will be defined as any toxicity occurring during the study that meets the criteria below. Toxicity that is clearly and directly related to the primary disease or to another etiology is excluded from this definition. The following will be unacceptable toxicities:

- Any Grade 4 irAE
- Any \geq Grade 3 colitis
- Any Grade 3 or 4 non-infectious pneumonitis irrespective of duration
- Any Grade 2 pneumonitis that does not resolve to \leq Grade 1 within 3 days of the initiation of maximal supportive care
- Any Grade 3 irAE, excluding colitis or pneumonitis, that does not downgrade to Grade 2 within 3 days after onset of the event despite optimal medical management including systemic corticosteroids or does not downgrade to \leq Grade 1 or baseline within 14 days
- Liver transaminase elevation $> 8 \times$ ULN or total bilirubin $> 5 \times$ ULN (other than the 1st week following DEB-TACE)

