In order to minimize the need for research-only in-person visits, telemedicine visits may be substituted for in-person clinical trial visits or portions of clinical trial visits where determined to be appropriate and where determined by the investigator not to increase the participants risks. Prior to initiating telemedicine for study visits the study team will explain to the participant, what a telemedicine visit entails and confirm that the study participant is in agreement and able to proceed with this method. In the event telemedicine is not deemed feasible, the study visit will proceed as an in-person visit. Telemedicine visits will be conducted using HIPAA compliant method approved by the Health System and within licensing restrictions.

- a. DEB-TACE will be repeated every 8 weeks as long as there is residual tumor that can be targeted after the first dose (we expect most patients will receive at least 2 doses, and more than 3 doses of DEB-TACE are possible). Patients with a complete response by mRECIST will stop DEB-TACE and continue the rest of the study regimen. When DEB-TACE will no longer be given, the entire DEB-TACE visit and evaluations (e.g. Week 16) and follow-up visit 1 week after the skipped DEB-TACE (e.g. Week 17) may be dropped.
- b. Full physical examination at baseline; targeted physical examination at other time points
- c. Patients will have their blood pressure and pulse measured before, during, and after the infusion at the following times (based on a 60-minute infusion):
 - At the beginning of the infusion (at 0 minutes)
 - At 30 minutes during the infusion (\pm 5 minutes)
 - At the end of the infusion (at 60 minutes \pm 5 minutes)
- d. for AEs/SAEs reported during prescreening additional information such as medical history and concomitant medications may be needed.

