11.2.4 Safety run-in

To ensure that the combination is safe, the first six patients will be treated and observed for toxicity for 1 cycle before continuation with further accrual. If ≤ 1 limiting toxicity events occur in the first 6 patients, we will proceed with additional accrual to complete a total of 20 patients for the safety evaluation. If >1 limiting toxicity events occur among the first 6 patients, then three additional patients will be enrolled (i.e. a total of 9 patients). If ≤ 2 limiting toxicity events occur in the 9 patients, we will proceed with additional accrual to complete a total of 20 patients for the safety evaluation. If > 2 limiting toxicity events occur, we will pause the enrollment pending safety review.

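### The run-in's proceed/pause rule closes at Week 6, before any repeat DEB-TACE at Week 8, so no cohort-level check covers embolization of patients already on immunotherapy

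*Combined protocol and SAP*

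**What the plan says.** Section 2.2 gives the secondary objective: "To assess the safety of combining DEB-TACE with durvalumab and tremelimumab in patients with intermediate stage HCC". Section 11.2.4 introduces the run-in as the means of ensuring that the combination is safe, and says "the first six patients will be treated and observed for toxicity for 1 cycle before continuation with further accrual". The rule has two steps. With at most 1 limiting event in 6 patients, accrual proceeds. With more than 1, three patients are added, and accrual then proceeds with at most 2 events in 9 and pauses for safety review with more than 2. The synopsis repeats this.

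Section 6.3 sets the counting window: "Unacceptable toxicities will be evaluated from the time of first administration of durvalumab or tremelimumab until the Week 6 evaluation", which it places "prior to the second dose of durvalumab". Its liver-test criterion carries an exemption, "other than the 1st week following DEB-TACE".

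On the schedule, Section 5.2.1 says "All patients in this study will receive durvalumab and tremelimumab 2 weeks after initial DEB-TACE treatment" and has immunotherapy continue alongside DEB-TACE every 8 weeks where targetable tumor remains. Footnote a to Figure 2 says "DEB-TACE will be repeated every 8 weeks as long as there is residual tumor that can be targeted after the first dose" and expects most patients to have at least two sessions. Section 3 places the third biopsy, after two durvalumab doses, "during their second DEB-TACE procedure at week 8, unless the patient has CR". Section 8.1.2 estimates up to four sessions in a year.

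**The concern.** The regimen contains two different exposures. One is immunotherapy started after a single embolization. The other is embolization of a liver already under checkpoint blockade. The run-in observes the first and closes before the second begins. Hepatic events are on the protocol's own list of events of special interest (Section 10.1.3), and Section 1.3.5.1 says that no clinical data on the 300 mg tremelimumab regimen were available when the protocol was drafted.

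At stake is what a passed run-in means. If limiting toxicity appears mainly after the second DEB-TACE, the run-in returns the same answer however frequent that toxicity is. Accrual then continues towards 20 patients, 14 of them beyond the first six, with no numerical rule that looks across patients at that exposure.

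**Working it through.** **Timing**

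| Event | Nominal | Limits with +/-7 days (Figure 2) |
|---|---|---|
| First DEB-TACE | Week 0 | none shown |
| First durvalumab + tremelimumab; window opens | Week 2 | Weeks 1 to 3 |
| Week 6 evaluation; window closes | Week 6 | Weeks 5 to 7 |
| Second DEB-TACE, if targetable tumor remains | Week 8 | Weeks 7 to 9 |
| AE check | Week 9 | none shown |
| AE check and chemistry | Week 10 | Weeks 9 to 11 |

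The plan's own figure reproduces: Week 2 plus one 4-week cycle is Week 6, so Sections 6.3 and 11.2.4 agree. The nominal gap to the second DEB-TACE is 8 - 6 = 2 weeks. At the extremes of the visit windows (6 + 1 and 8 - 1) the two meet at Week 7, which leaves no observation time after a repeat DEB-TACE inside the window.

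**Cohort clock**

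Assume even accrual of 22 patients over the 12 months planned in Section 3: 52/22 = 2.4 weeks per patient. The sixth patient starts at 5 x 2.36 = 11.8 weeks and reaches Week 6 at 17.8 weeks. The fifth started at 4 x 2.36 = 9.5 weeks and is then 8.4 weeks in. So some run-in patients would probably have had a repeat DEB-TACE before the decision. Those events are recorded, but they fall outside the stated window and do not count.

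**Size**

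The documents give no operating characteristics for the run-in and no toxicity rates, so the rates r below are assumptions. Also assumed: at most one limiting event per patient, independence between patients, and every patient re-treated. If the 6-then-9 rule were applied to events after the second DEB-TACE:

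P(pause) = P(X6 >= 3) + P(X6 = 2) x P(X3 >= 1), with X6 ~ Bin(6, r) and X3 ~ Bin(3, r).

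| r | P(X6 >= 3) | P(X6 = 2) | P(X3 >= 1) | P(pause) | P(X6 > 1): adds three patients only |
|---|---|---|---|---|---|
| 10% | 0.016 | 0.098 | 0.271 | 0.043 | 0.114 |
| 20% | 0.099 | 0.246 | 0.488 | 0.219 | 0.345 |
| 30% | 0.256 | 0.324 | 0.657 | 0.469 | 0.580 |
| 40% | 0.456 | 0.311 | 0.784 | 0.700 | 0.767 |

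If only 70% of patients are re-treated (also an assumption), the rate per run-in patient is 0.7r, that is 7%, 14%, 21% and 28%. The same formula then gives P(pause) of 0.017, 0.098, 0.242 and 0.418.

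Under the current window these events contribute nothing. P(pause) depends only on the Week 2 to Week 6 rate: 0.7% if that rate is 5%, 4.3% if 10%, 11.5% if 15%, whatever happens after Week 8.

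**The case against.** The case against is substantial, and parts of it stand.

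- **Later safeguards exist.** A reader might infer that no toxicity limit applies to anyone after the run-in. The documents do not support that. Section 4.3 makes unacceptable toxicity, and AEs meeting the Appendix 1 criteria, grounds for permanent discontinuation, with no Week 6 cutoff. Section 10.3.11 requires SAE reports within 24 hours. Section 13.1 requires safety concerns to go immediately to the IRB and the sponsor, and Section 14.1 describes ongoing company monitoring. The narrower statement survives: no later cohort-level threshold appears in the visible text. Section 6.4 and Appendix 1 are not visible in full.
- **The objective has data.** A reader might infer that repeat-DEB-TACE safety goes unmeasured. It does not: AEs are collected to 90 days after the last dose (Section 10.3.1) and tabulated for the safety set (Section 11.2.1). Only the proceed/pause decision is blind to these events.
- **The liver exemption is not a mismatch.** It has essentially no effect inside the run-in window, because the only earlier DEB-TACE is at Week 0. But the same toxicity list also serves individual discontinuation throughout the study, where the exemption applies after every repeat session.
- **The size is easy to overstate.** The last column of the table (11% to 77%) is the chance of adding three patients, not of pausing. Repeat DEB-TACE is also conditional, so the figures for every patient re-treated are upper values.
- **One cycle is a legitimate choice.** It covers the single tremelimumab dose, and the two sections agree on it. This is a limit on what the run-in can show, not an arithmetical error.

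**Conclusion.** The point holds as a gap in coverage. The only cohort-level proceed/pause rule in the visible text ends, on each patient's own clock, before the first DEB-TACE given under immunotherapy, which the protocol expects most patients to receive. A passed run-in therefore clears first-cycle immunotherapy after one embolization and says nothing about repeat embolization.

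Applied to events after repeat DEB-TACE, the existing rule would pause accrual with probability of about 4%, 22%, 47% and 70% at rates of 10%, 20%, 30% and 40%, and less if some patients are not re-treated. These figures illustrate the rule under the assumptions stated; they do not predict toxicity. The timing conclusion needs no assumed rate. A change is worth making because the data are already scheduled and the cost is low. The individual-patient safeguards and the final safety analysis are not in question.

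**What to change.** Keep the Week 6 count. In Sections 6.3 and 11.2.4 (and the synopsis) add a second cohort-level count:

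- **Who:** the same run-in patients, limited to those who receive a second DEB-TACE. Report the others, for example patients in CR, separately. If the run-in closed at six, more than 1 event in this count extends it to the next three patients accrued, as in the present rule.
- **When:** at the first scheduled visit with chemistry after the exempt first week following the actual second DEB-TACE, nominally Week 10. Time it from the procedure, because the +/-7-day windows can bring the two visits together. Week 9 would not serve: Figure 2, as extracted, shows an AE check then but no chemistry panel.
- **What:** the existing toxicity list and attribution exclusions.
- **Limit:** state that more than 2 events in 9, not more than 1 in 6, triggers the pause pending safety review already described. Accrual continues meanwhile. At the even rate above, about 4/2.36 = 1.7 patients would be enrolled between the sixth patient's Week 6 and Week 10.

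Section 6.3 also describes unacceptable toxicity as arising at any time in the study, beside a window that ends at Week 6. Reconcile the two by separating the run-in count from the study-long use for individual discontinuation. Section 4.3 should then point to that definition; it now cites Section 6.5, which the table of contents does not list.

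The cost is protocol wording, one extra review of data already scheduled, and a small chance of a later, possibly unnecessary, pause (about 4% if the true rate is 10%). No visit, dose, schedule or individual stopping rule changes. If the sponsor keeps the present window, the protocol should say that the run-in does not cover repeat DEB-TACE and how that toxicity will be reviewed across patients.

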6.4 Dose modification and toxicity management

6.4.1 Durvalumab and tremelimumab

7. RESTRICTIONS DURING THE STUDY AND CONCOMITANT TREATMENT(S)

7.1 Restrictions during the study

The following restrictions apply while the patient is receiving study treatment and for the specified times before and after:

Female patient of child-bearing potential

Females of childbearing potential who are sexually active with a non-sterilized male partner must use at least 1 **highly** effective method of contraception (Table 1) from the time of screening and must agree to continue using such precautions for 180 days after the last dose of durvalumab + tremelimumab combination therapy or 90 days after the last dose of durvalumab monotherapy. Non-sterilized male partners of a female patient must use male condom plus spermicide throughout this period. Cessation of birth control after this point should be discussed with a responsible physician. Not engaging in sexual activity for the total duration of the drug treatment and the drug washout period is an acceptable practice; however, periodic abstinence, the rhythm method, and the withdrawal method are not acceptable methods of birth control. Female patients should also refrain from breastfeeding throughout this period.

Male patients with a female partner of childbearing potential

Non-sterilized males who are sexually active with a female partner of childbearing potential must use a male condom plus spermicide from screening through 180 days after receipt of the final dose of durvalumab + tremelimumab combination therapy or 90 days after receipt of the final dose of durvalumab monotherapy. Not engaging in sexual activity is an acceptable practice; however, occasional abstinence, the rhythm method, and the withdrawal method are not acceptable methods of contraception. Male patients should refrain from sperm donation throughout this period.

Female partners (of childbearing potential) of male patients must also use a highly effective method of contraception throughout this period (Table 1).

Females of childbearing potential are defined as those who are not surgically sterile (i.e., bilateral tubal ligation, bilateral oophorectomy, or complete hysterectomy) or post-menopausal.

Women will be considered post-menopausal if they have been amenorrheic for 12 months without an alternative medical cause. The following age-specific requirements apply:

- Women <50 years of age would be considered post-menopausal if they have been amenorrheic for 12 months or more following cessation of exogenous hormonal treatments and if they have luteinizing hormone and follicle-stimulating hormone levels in the post-menopausal range for the institution or underwent surgical sterilization (bilateral oophorectomy or hysterectomy).

- Women ≥ 50 years of age would be considered post-menopausal if they have been amenorrheic for 12 months or more following cessation of all exogenous hormonal treatments, had radiation-induced menopause with last menses >1 year ago, had chemotherapy-induced menopause with last menses >1 year ago, or underwent surgical sterilization (bilateral oophorectomy, bilateral salpingectomy or hysterectomy).

Highly effective methods of contraception, defined as one that results in a low failure rate (i.e., less than 1% per year) when used consistently and correctly are described in Table 1. Note that some contraception methods are not considered highly effective (e.g., male or female condom with or without spermicide; female cap, diaphragm, or sponge with or without spermicide; non-copper containing intrauterine device; progestogen-only oral hormonal contraceptive pills where inhibition of ovulation is not the primary mode of action [excluding Cerazette/desogestrel which is considered highly effective]; and triphasic combined oral contraceptive pills).

Table 1. Highly effective methods of contraception (<1% failure rate)

Barrier/Intrauterine methods	Hormonal Methods

• Copper T intrauterine device• Levonorgestrel-releasing intrauterine system (e.g., Mirena®)^a	
• Implants: Etonogestrel-releasing implants: e.g. Implanon® or Norplant®• Intravaginal: Ethinylestradiol/etonogestrel-releasing intravaginal devices: e.g. NuvaRing®• Injection: Medroxyprogesterone injection: e.g. Depo-Provera®• Combined Pill: Normal and low dose combined oral contraceptive pill• Patch: Norelgestromin/ethinylestradiol-releasing transdermal system: e.g. Ortho Evra®• Minipill: Progesterone based oral contraceptive pill using desogestrel: Cerazette® is currently the only highly effective progesterone based pill

^a This is also considered a hormonal method

Blood donation

Patients should not donate blood while participating in this study.

7.2 Concomitant treatment(s)

The Principal Investigator must be informed as soon as possible about any medication taken from the time of screening until the end of the clinical phase of the study (final study visit). Any concomitant medication(s), including herbal preparations, taken during the study will be recorded in the CRF.

Restricted, prohibited, and permitted concomitant medications are described in the following tables. Refer to **Section 6.4** for guidance on management of IP-related toxicities.

7.2.1 Antiviral Therapy for HBV+ Patients

Patients with HBV infection, characterized by positive hepB surface antigen (HBsAg) and/or HepB core antibodies (anti-HBc) with detectable HBV DNA (≥ 10 IU/ml or above the limit of detection per local lab standard), must be treated with antiviral therapy as per institutional practice to ensure adequate viral suppression (HBV DNA ≤ 2000 IU/mL) prior to enrollment. Patients must remain on antiviral therapy for the study duration and for 6 months after the last dose of study medication. These subjects will be tested at every cycle to monitor HBV DNA levels

Patients who test positive for anti-hepatitis B core (anti-HBc) with undetectable HBV DNA (< 10 IU/ml or under the limit of detection per local lab standard) do not require anti-viral therapy prior to enrollment. These subjects will be tested at every cycle to monitor HBV DNA levels and initiate antiviral therapy if HBV DNA is detected (≥ 10 IU/ml or above the limit of detection per local lab standard). HBV DNA detectable subjects must initiate and remain on antiviral therapy for the study duration and for 6 months after the last dose of study medication.

